# Exploratory Analysis (Specific Aims 1 & 2):

# Daily: Follow-up online message data on marijuana use and pain during 2-week period of ad libitum use

Multilevel modelling via random coefficient regression (PROC MIXED or PROC GLIMMIX in SAS Version 9.4) will be used to test between and within-participant relationships between marijuana use and pain in daily message data. Conditional models will be specified with random and fixed effects of marijuana use (modelled as either yes/no for daily use or as quantity of use) predicting pain intensity or pain interference. To account for repeated measures over time, an autoregressive covariance structure will be used for all models. For the continuous quantity of use measure, following Wang and Maxwell, between- and within-participant effects will be disaggregated by person mean-centering the marijuana quantity variable (subtracting the average quantity of marijuana use for that individual), and including time (in days since baseline) as a covariate to detrend the outcome variable (pain intensity/pain interference) in case there are any linear trends in pain over time. The test of the fixed effect of the person mean-centered marijuana quantity variable indicates whether on average there is a significant within-participant relationship between marijuana quantity of use and pain. The test of the fixed effect of the person-mean marijuana quantity (each individual's own average marijuana quantity) indicates whether there is a between-participant relationship of marijuana quantity of use to pain intensity/interference. Due to the intensive longitudinal nature of the design, we will have more than enough power with n=246 participants to estimate these models. In addition, the random coefficient regression procedures allow us the capability of using modern approaches to the handling of missing data including full information maximum likelihood estimation.

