We propose to examine the effects of cannabinoids in edible form on pain relief, inflammation, and cognitive dysfunction in chronic low back pain patients who choose to use marijuana in the context of a short-term (2 weeks) mechanistic study using a patient-oriented, observational design and a Mobile pharmacology and phlebotomy lab that solves many of the logistical problems with marijuana research. Our global hypothesis is that our observations of self-report and objective measures of the effects of marijuana edible products by pain patients who choose to use these products will vary as a function of the levels of THC to CBD in their blood. Further, we hypothesize that cognitive impacts observed will differ by the THC/CBD levels in blood. To that end, we will measure the association of pain, inflammation, and cognitive impairment with the levels of THC and CBD in the blood of pain patients who wish to use edible cannabis to treat their pain. This approach is ecologically valid and timely given that edibles of various cannabinoid ratios are widely used by patients in state legalized markets, yet absolutely no research has been done on these products. Edibles generally have either THC-only, CBDonly, or include both THC and CBD. Recent data, including our pilot work, suggest that THC and CBD together produce unique effects on pain, inflammation, and cognition. We will use a patient-oriented, observational design, in which chronic low back pain patients who self-initiate the use of a marijuana edible to manage their pain are observed over their 2-Week study period while using a product of their choosing. THC and CBD blood levels will be tested in relation to all outcomes.

Page 2 of 34

**Aim 1.** To investigate the mechanisms that may underlie the widespread use of marijuana among pain patients in a 2-week observational study of ad-libitum use, we will observe whether there is an association between cannabinoid levels in blood and measures of self-reported pain.

Hypothesis 1. Based on numerous studies that suggest CBD and THC may work together to produce the analgesic effects of marijuana, we hypothesize that higher blood levels of both THC and CBD will have the strongest association with lower levels of **pain interference** after 2 weeks.

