# Marijuana Administration at Home

The proposed work will utilize a design that is observational and does not involve assignment by the research team. More specifically, patients who are already planning to try marijuana as a treatment for their pain will choose their own product at baseline and inform staff of their choice. The patient will then purchase the product at a dispensary. The patient will be observed before they purchase and begin using their product (Baseline Appointment), during use (Daily follow-up messages), and after 2-weeks (2-Week Appointment) of using their product ad libitum at home. After the 2-Week Appointment, we will complete Monthly follow-up surveys with the patient for 6 months to determine what additional products the patient may have tried and to collect self-report information on product use and current levels of pain.

Specifically, at the end of the Baseline Appointment, individuals will be asked to select and purchase an edible marijuana product to use ad libitum for the next 2 weeks. Colorado requires all edibles to be tested by a state lab, which allows us to have a precise measure of potency after the participants purchase their products. Importantly, the researchers who conduct the assessments as well as all the senior investigators will be blind to the participant's product choice. Participants will use their selected product at home consistent with the packaging directions, direction from their physician, or as they see fit, and will be asked not to use any other marijuana product during the 14 days before their 2-Week Appointment (with one Pre- and two Post-administration mobile assessments on the final day of the 2-week ad libitum study period). Study staff will not provide any directions regarding dosing and administration.

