# Monthly: Follow-up online survey data on marijuana use and pain after 2-week period of ad libitum use

The prospective data we are collecting on a monthly basis for six months after the 2-week ad libitum phase allows for the possibility of changes in marijuana use over time and tests of the extent to which those changes vary with changes in pain intensity or pain interference. We do not have a priori hypotheses about what will occur during this six-month time frame so these analyses are exploratory in nature. In order to explore these data, we envision that the primary version of this analysis would be parallel process latent growth modeling (LGM). With this analytic strategy we can statistically test whether the change in frequency or quantity of marijuana use (slope) over time is positive or negative, whether the change in pain is positive or negative, and whether there is an association between the slope in change of marijuana use and pain over time. Importantly, should edible groups arise in our data, it is also possible to conduct a cross-groups parallel process LGM in which the model is simultaneously estimated and the moderation of each path in the model can be examined to determine whether it differs in the groups. For example, we could stratify the analyses by type of marijuana product chosen by the participant (high THC versus low THC), and then test the model of marijuana use and pain as a crossgroups model by marijuana use characteristics. These analyses, while exploratory, will provide important naturalistic data on marijuana use among chronic pain patients over time, and lay critical groundwork for future studies in this area. We have estimated similar models with ~200 participants, so we anticipate adequate power for these exploratory models in the current study. Further, LGM incorporates full

information maximum likelihood of missing data, which allows us to maximize the sample size. Because these analyses are exploratory, we will also examine graphical presentations of growth curves in addition to traditional null hypothesis significance tests.

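### The exploratory daily model uses one undifferentiated quantity of marijuana as its exposure, so its coefficients average over THC-only, CBD-only and mixed edibles and cannot separate the two cannabinoids

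*Combined protocol and SAP*

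**What the plan says.** The daily subsection of the Exploratory Analysis models pain with "random and fixed effects of marijuana use (modelled as either yes/no for daily use or as quantity of use"). Quantity is split by "person mean-centering the marijuana quantity variable (subtracting the average quantity of marijuana use for that individual") to give a within-participant term, and the "person-mean marijuana quantity (each individual's own average marijuana quantity") gives the between-participant term. No unit is stated for quantity. There is no conversion to mg of THC or CBD, no product-type covariate and no product interaction.

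Three other places bear on this:

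- **Products differ in kind.** The Objectives section states: "Edibles generally have either THC-only, CBDonly, or include both THC and CBD".
- **Potency is available for the two-week product.** The section on Marijuana Administration at Home says that Colorado requires edibles to be tested, "which allows us to have a precise measure of potency after the participants purchase their products". It also asks participants to use no other marijuana product over the 14 days.
- **Amount is recorded.** Table 1 lists amount, strain and method among the daily items.

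The monthly subsection models "whether the change in frequency or quantity of marijuana use (slope) over time is positive or negative". It also offers a cross-groups model if edible groups emerge, with high versus low THC as its example.

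**The concern.** The protocol's central idea is that effects depend on THC and CBD separately. The primary models for Hypotheses 1 to 3 follow that idea by entering blood THC, blood CBD and their interaction. The protocol also concedes that it does not control product or dosing, and it answers this with blood levels. Blood is drawn only at Baseline and at the 2-Week Appointment, so that answer does not reach the daily data. There, the plan falls back on a single quantity and does not use the potency information it says it will have.

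One unit of a CBD-only product and one unit of a THC-only product then count as the same exposure. A quantity slope near zero could mean that neither cannabinoid is related to pain, or that two relationships cancel. A clearly negative slope could come from either cannabinoid or from both. Because the unit is unspecified, the coefficient would also be hard to compare with any other study. The protocol presents the daily data as informative on the impact of edibles on pain, so the coefficient should be interpretable.

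**Working it through.** **Plan figures.** The daily section gives no effect size or power calculation. It only asserts that 246 participants are more than enough. The one computed power figure belongs to the primary regression: noncentrality 0.04 × 246 = 9.84 with 1 and 242 degrees of freedom gives 0.878, matching the stated .88. It says nothing about how daily exposure is defined.

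**What the between-person term compares.** Take 10 mg units. Participant A takes 2 units a day of a THC-only product and participant B takes 2 units a day of a CBD-only product. Both have a person-mean quantity of 2. A has 20 mg THC and 0 mg CBD; B has 0 mg THC and 20 mg CBD. If unit strength also varies, 2 units may be 2 × 5 = 10 mg or 2 × 20 = 40 mg. The model sees no difference.

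**What the pooled slope estimates.** All inputs here are assumed; none is in the documents. Products are equal thirds THC-only, CBD-only and 1:1. Each active cannabinoid changes pain by 0.3 points in size per 10 mg. Choice of product and strength is unrelated to units taken. The pooled slope per unit is then the average of the product-specific slopes:

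| Scenario | THC-only | CBD-only | 1:1 | Average per unit |
|---|---|---|---|---|
| Only THC active, 10 mg units | -0.30 | 0 | -0.15 | -0.15 |
| Both act alike, 10 mg units | -0.30 | -0.30 | -0.30 | -0.30 |
| Opposite effects, 10 mg units | -0.30 | +0.30 | 0 | 0.00 |

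With units of 5, 10 or 20 mg in equal shares, mean strength is 35/3 = 11.67 mg. The first two rows are then multiplied by 1.167, giving about -0.175 and -0.35.

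A simulation of the within-person term (246 people, 14 days, Poisson 1.5 units per day, residual SD 1.5, 500 runs, common slopes) gave -0.15, -0.30 and 0.00 for 10 mg units, and -0.18 and -0.35 for 5/10/20 mg units. Person-centred mg THC and mg CBD entered together returned -0.30 per 10 mg for THC and 0.00, -0.30 or +0.30 for CBD, as set.

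**Does spread in potency alone shrink the slope?** Write log mg = log units + log potency, with potency independent of units and a true slope b on log mg. The slope on log units is b × cov(log mg, log units) / var(log units) = b. With log-SD 0.4 to 0.8 for units and 0.4 to 1.0 for potency, units share only 14% to 80% of the variance of log mg (for example 0.16/(0.16 + 1.00) = 0.14). Even so, the fitted slope in simulation stayed between -0.296 and -0.302 against a true -0.30. Such spread costs precision; it does not bias the slope.

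**What separates THC from CBD.** For a participant on one mixed product, both mg values are fixed multiples of amount and so perfectly collinear. For a participant on a single-cannabinoid product, one of them is always zero. Within-person separation therefore comes from comparing product groups, under the assumption that slopes per mg are the same across them.

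**The case against.** The strongest reply has four parts.

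1. **The average is the stated target.** The plan describes the within-participant test as an average relationship and speaks of quantity, not dose. It does not say that quantity means raw units. This is fair. But an average over unlike products still cannot be read without the product mix, and even total mg would not separate THC from CBD.
2. **Random slopes already absorb product differences.** The model has "random and fixed effects of marijuana use", and each participant is asked to keep to one product. This makes the within-person term less exposed than the between-person term. Nothing links the slope variation to product, however, and the fixed effect remains a pooled average.
3. **The THC and CBD hypotheses are tested in blood.** This stands. The daily analysis is not the test of those hypotheses and is labelled exploratory.
4. **Mg terms do not give a clean separation.** This also stands, for the collinearity reason shown in the working, and it should be stated with the results.

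A reader might also infer that differences in potency attenuate the quantity slope. That does not follow when potency is independent of units. The documents say nothing about how the two are related.

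A reader might further extend the whole criticism to the monthly model. The documents do not support that. Tested potency is described only for the product bought for the two weeks, the monthly result is an association between slopes, and the high versus low THC split is offered as an example of an open option.

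**Conclusion.** The point holds for the daily model as one of composition and interpretability. The quantity coefficient mixes cannabinoids and strengths, cannot separate THC from CBD, and can be near zero when both matter. In the illustration it ran from 0.00 to -0.35 per unit while each active cannabinoid's effect was always 0.3 in size per 10 mg. Those values rest on assumed product shares, strengths, effects and independence of product from amount. They show what can happen, not what will.

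The point does not support a claim of bias from potency spread alone. For the monthly model, what remains is that the optional product split leaves CBD out of its example and depends on groups emerging. Materiality is low: both analyses are exploratory, and the primary blood-level analyses do not depend on them. It is a cheap improvement.

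**What to change.** **Daily model.** State the unit of quantity. Make daily mg THC and daily mg CBD the main quantity measures, computed as reported amount × tested potency of the purchased product. Give each a person-mean-centred and a person-mean term. Keep raw quantity as a sensitivity analysis. Flag days with unknown potency or with use of another product, and say how they are handled. State in the plan, and with the results, that separating the THC and CBD slopes relies on comparing self-selected product groups.

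**Monthly model.** Keep frequency or quantity as the growth process, because potency of later products is not documented. Define the optional stratification by two-week product type (THC-only, CBD-only or both) where group sizes allow.

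**Cost.** Wording in the analysis plan and one derived data set from items already planned for collection. The model gains extra terms, and the daily amount must be recorded in a form that converts to mg.

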#### IV. RESEARCH STUDY DESIGN

Overview and Design of the Proposed Study

A sample of 289 patients who report chronic (at least 12 weeks) low back pain and the intention to try marijuana products for pain relief will be collected. Although the origin of chronic pain is heterogeneous and diagnostically complex, with subjective, affective, and cognitive components, self-report is the backbone of a medical diagnosis. Thus, we rely on self-report of pain intensity and duration for inclusion decisions for our study. Participants need to have at least one instance of lifetime marijuana use, but must have less than weekly marijuana use for the prior six months. Additionally, participants must not have used marijuana at *any time* for the treatment of their pain. As such, participants will be naïve to the use of marijuana for pain, but not to marijuana consumption in general. Recruitment will be via a number of sources that have been used successfully by our research team (described below). If the patient meets minimum eligibility criteria (also described below) and is interested in participating, they will set up an appointment to come to the CU Change Lab for their Baseline Appointment (1st Appointment) involving consent, extensive measures of health behavior (e.g., substance use, sleep quality, physical function, mood, health history, etc.), a blood draw to determine cannabinoid levels and biomarkers of inflammation, and baseline assessments of their low back pain and cognitive function.

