# **Specific Aim 1:**

# **Hypothesis 1**

**Objective 1:** We will observe levels of pain in individuals with chronic low back pain who engage in 2 weeks of *ad libitum* use of marijuana edible product of their choice with various cannabinoid content. *Hypothesis 1* predicts that observed THC and CBD blood levels will impact lower levels of low back pain interference after 2 weeks, compared to THC or CBD blood levels considered in isolation.

**Primary endpoint/analysis**: The Roland Morris Disability Questionnaire (RMDQ) has been used in studies of low back pain and asks participants about how their experience of low back pain interfered with 24 daily activities in the past two weeks; total score ranges from 0-24. Using the total RMDQ score, we will test pain interference using two time points – Baseline (prior to taking any cannabis) and 2-Week Pre-administration (after 2 weeks of product use but immediately before last edible use in the 2-Week study period). We will test a ordinary least squares (OLS) regression model in which blood levels of CBD, THC, and the CBDxTHC interaction are used to predict 2-Week pre-administration pain interference controlling for Baseline pain interference. Note that our participants are naïve to recent cannabis use at Baseline (per our eligibility criteria) so it is not necessary to control for Baseline levels of cannabinoids. Thus we are testing the effect of blood levels of cannabinoids on experience of recent pain interference. We predict that higher levels of THC and CBD will be associated with less pain interference.

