### XXVI. SHARING OF RESULTS WITH PARTICIPANTS

There are no plans to share results of the study with participants.

Table 4.			Schedule of	Evaluatio	ns		
		Baseline Visit 1:	Daily:		2- Week Visit 2:		Monthly:
Assessment:	Phone/ Online	Enrollment, Randomization, Observation <pre-2w sa=""></pre-2w>	Follow-up Surveys	<pre-0h SA></pre-0h 	Observation <post-1h sa=""></post-1h>	n <post-2h SA></post-2h 	Follow-up Surveys
	(d: -14)	(d: 1)	(d: 2-15)	(d: 16)	(d: 16)	(d: 16)	(d: 30+)
	(w: -2)	(w: 1)	(w: 1-2)	(w: 2)	(w: 2)	(w: 2)	(w: 4+)
							(m: 1-6)
Time point		In-Person (1d) 1 time point	Online (14d) 14 time points	In-Person (1d) 3 time points		Online (6m) 6 time points	
Eligibility Screening Form/Scheduling (Inclusion/Exclusion Criteria Table 2)	X	X					
Physician Review (If needed for eligibility or safety concerns)	X						
Informed Consent Form/Enrollment		X					
Breathalyzer/Alcohol Content Test		X		X			
Blood Pressure (BP)		X		X	X	X	
Physiological Weight Scale		X		X			
Stadiometer (Height)		X					
Medical History & Prescribed Medication Use		X		X*			X*
Urine Analysis (Pregnancy & Toxicology)		X					
Demographics (D)		X		_			
Alcohol Use History (AUH)		X					
Alcohol Use Disorder Identification test (AUDIT)		X					
Marijuana Purchasing Task (MPT)		X		X			
Beck Depression Inventory-II (BDI-II)		X					
Beck Anxiety Scale (BAI)		X		_			

ADHD Self-Report Scale (ASRS)	X				
Pain Intensity (PIT7)	X	X			X
Pain Interference (PIF7)	X	X			X
Marijuana Dependence Scale (MDS)	X	X			X
Marijuana users Cohort (MUHC)	X*				
Impact of Marijuana on Pain (IMP)	X	X*			X*
Health Related Questionnaire (HRQL/SF-12)	X	X			X
*Time Line Follow Back (TLFB)	X	X			X
Pittsburg Sleep Quality Index (PSQI)	X	X			X
*Roland Morris Disability Questionnaire (RMDQ)	X	X			X
Depression Anxiety Stress Scale (DASS)	X	X			X
Self-Rated Diet (SRD)	X	X			X
Functional Assessment of Cancer Therapy – Cognitive Function (FACT-Cog)	X	X			X
Current Opioid Misuse Measure (COMM)	X	X			X
The Drug Effects Questionnaire (DEQ)		X	X	X	
The Addiction Research Center Inventory (M-Scale)		X	X	X	
Heart Rate (HR)	X	X	X	X	
Venous Blood Draw (BD)	X	X	X	X	
Pain Intensity-current (PITc)	X	X	X	X	X
*Pain Interference-current (PIFc)	X	X			X
Motor/Movement Battery (MB)	X	X	X	X	
International Shopping List Test (ISLT)	X	X	X	X	
Neurocognitive Toolbox Battery (NCB)	X	X	X	X	
Marijuana Craving Questionnaire (MCQ)	X	X	X	X	
Alcohol Craving Questionnaire (ACQ)	X	X	X	X	
*Profile of Mood States (POMS)	X	X	X	X	

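### The exploratory daily model tests each person's mean marijuana quantity against pain without the Baseline pain already collected, so pre-use severity may bias the between-person coefficient

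*Combined protocol and SAP*

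**What the plan says.** The Daily subsection of the Exploratory Analysis states: "Conditional models will be specified with random and fixed effects of marijuana use", predicting pain intensity or pain interference. For quantity of use, it splits the predictor into a person mean and a person-mean-centred daily value, "including time (in days since baseline) as a covariate to detrend the outcome variable". The person-mean term "indicates whether there is a between-participant relationship of marijuana quantity of use to pain intensity/interference". No other covariate is named. On power it says only "we will have more than enough power with n=246 participants to estimate these models".

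Baseline pain is available. The Section IV overview lists "baseline assessments of their low back pain and cognitive function" at the first appointment. Table 3 describes PIT7 (average and worst pain over 7 days, 0 to 10), PIF7 (7-day interference, 1 to 5) and a current pain item (0 to 10), and Table 4 schedules all three at Baseline. Participants buy and start the product after that visit, and the daily messages begin after purchase.

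The primary analysis for Hypothesis 1 predicts the 2-week score "controlling for Baseline pain interference". The primary analyses for Hypotheses 2 and 3 adjust for their baseline outcomes in the same way.

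**The concern.** Study staff give no dosing directions. According to Marijuana Administration at Home, participants follow the packaging, their physician or their own judgement. Someone who starts with worse pain may take more, and will tend to report worse pain over the next 14 days whatever the product does. The person-mean coefficient would then mix any effect of use with severity that existed before use.

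Nothing in the specified model deals with this. Person-mean centring protects only the within-person term. The day covariate removes a time trend, not differences between people. A random person effect would assume that unexplained differences in pain level are unrelated to mean quantity, which is the assumption in doubt. The only wording elsewhere about covarying baseline differences is in Table 3 and concerns the BDI-II and BAI.

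At stake is the reading of an exploratory between-person result. If severity and quantity rise together, it could look like harm from marijuana or conceal a benefit.

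**Working it through.** **The plan's own figure.** Power Analysis and Sample Size Requirements gives power .88 at f² = .04 and N = 246, two-sided alpha .05. For one coefficient in a three-predictor regression, the noncentrality is .04 × 246 = 9.84, and the noncentral F (1 and 242 df) gives .878, so the figure reproduces. It belongs to the regression on blood THC, CBD and their product. No numerical power is given for the daily model.

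**Inputs.** N = 246 is from the Daily subsection. Two correlations are assumptions, because the documents give neither:
- r, between Baseline pain and person-mean quantity: 0, .1, .2, .3.
- ρ, between Baseline pain and person-mean daily pain: .5 and .7.

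Quantity has no true effect on pain.

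**Unadjusted test.** The correlation induced between mean quantity and mean daily pain is r × ρ. On the Fisher scale z = atanh(rρ) × √(246 − 3), and the two-sided rejection rate is Φ(z − 1.96) + Φ(−z − 1.96). For r = .2 and ρ = .5: rρ = .10, z = .1003 × 15.59 = 1.56, rejection 35%. For r = .3 and ρ = .7: rρ = .21, z = .2132 × 15.59 = 3.32, rejection 91%.

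| r | ρ = .5 | ρ = .7 |
|---|---|---|
| 0 | 5% | 5% |
| .1 | 12% | 19% |
| .2 | 35% | 59% |
| .3 | 65% | 91% |

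For r above 0, nearly all rejections are in the direction of more marijuana with more pain. With r = −.2 the rates are the same as for +.2, but the direction is reversed.

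**Check with daily data.** A simulation of 246 people over 14 days, with autocorrelated errors, no true effect and 2,000 runs per setting, regressed person-mean pain on person-mean quantity. Here ρ (.5 to .7) refers to the underlying pain level, so the rates are slightly lower: 12–18% at r = .1, 32–53% at .2 and 63–88% at .3. With Baseline pain added, rejection was 4–5% in every setting. The standard error of the quantity coefficient fell from about .065 to .048–.060, about 8–26%.

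**Masking.** With an assumed true coefficient of −.15 (benefit) and ρ = .6, the mean unadjusted estimate was −.03 at r = .2 and +.03 at r = .3, with about 8% rejection. Adjusted, it was −.146 with 74–76% rejection.

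**Imperfect Baseline measure.** Let r and ρ now refer to true severity, and let the Baseline score have reliability k. The adjusted coefficient for quantity, in standardised units, is then rρ(1 − k)/(1 − kr²), against rρ unadjusted. At r = .2 and ρ = .5, the bias falls from .10 to .021 with k = .8 (.10 × .2/.968) and to .041 with k = .6 (.10 × .4/.976). At r = .2 and ρ from .5 to .7, rejection falls from 35–59% to about 6–18%. Adjustment removes most of the bias, not all of it.

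**The case against.** The analysis is labelled exploratory, and the text speaks of a between-participant relationship, not an effect. An unadjusted coefficient answers that literal question. In the calculations above the marginal association is real, so the high rejection rates are not type I errors for a purely descriptive target. This stands, and it keeps the point minor. It does not justify leaving out the covariate: the Section IV overview says the daily tracking will inform the impact of the edible on pain, which invites an effect reading.

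The correlation between severity and quantity is also unknown. Packaging, physician advice and cost (about $90, paid by the participant) influence the amount taken as well, and the pain criterion in Table 2 may narrow the Baseline range and so shrink the bias. All of this stands. A reader might infer that severity is known to drive quantity, or that the bias must run toward harm. The documents support neither: at r = 0 there is no bias, and at negative r it runs toward benefit.

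A reader might also quantify the precision gain by dividing f² = .04 by 1 − ρ², which moves power from .88 to .95 (ρ = .5) or .99 (ρ = .7). The documents do not support this. That f² is for the blood-level regression, and the division assumes Baseline pain unrelated to quantity, contrary to the confounding scenario.

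Other secondary endpoints for Hypothesis 1 include two-week pain intensity, modelled on the same structure as appropriate, which may bring in baseline adjustment. That lowers the stakes but does not repair the daily quantity model.

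**Conclusion.** The omission is real and departs from the baseline adjustment in the three sets of primary models. Its effect depends on two correlations that the documents do not give. Over the ranges assumed here, with 246 people and no true effect, the unadjusted between-person test rejects from about 5% (no severity–quantity correlation) to 91% of the time (.3 and .7).

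It would be tempting to say that adjustment restores the 5% rate. That holds only if Baseline pain is measured without error and is the sole confounder. Pain during the 14 days may itself raise use, and a Baseline covariate does not address that. What can be said is that adjustment removes most of the bias from starting severity and reduces residual between-person variance.

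The within-person test is unaffected because centring removes stable differences between people, and no primary conclusion depends on this model. Severity is minor.

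**What to change.** In the daily-message models, add the grand-mean-centred Baseline value of the matching outcome as a person-level fixed covariate: the PIT7 average-pain rating for daily pain intensity, and PIF7 if pain interference is analysed. (The daily assessment description in Section XII lists only a Pain Intensity item, so the plan should also say whether daily interference will exist.) Take the person-mean quantity coefficient from this model, and report it as an association with possible residual confounding. Specify this before the outcome data are analysed.

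The cost is one sentence in the analysis plan, one model term and one degree of freedom. No new data or visits are needed.
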